1. ETHICAL CONDUCT OF THE STUDY AND REGULATORY REQUIREMENTS

1.1 Institutional Review Board (IRB)

The study protocol and any amendments will be reviewed by the Western Institutional Review Board (WIRB). The IRB will review the participant safety, informed consent form (ICF), their updates (if any), and any written materials given to the participants.

1.2 Ethical Conduct of the Study

This study will be conducted in accordance with the ethical principles that have their origins in the Declaration of Helsinki, in compliance with the approved protocol, Good Clinical Practice (GCP) and applicable regulatory requirements.

1.3 Participant Information and Consent

The investigator will obtain a freely given written consent from each participant after an appropriate explanation of the aims, methods, anticipated benefits, potential hazards, and any other aspects of the study that are relevant to the participant's decision to participate. In appropriate language, the consent form must be signed and dated by the participant before he/she is exposed to any protocol-specific procedure.

The investigator will explain that the participants are completely free to refuse to enter the study or to withdraw from it at any time, without any consequences for their further care and without the need to justify.

The participant will receive a copy of the signed informed consent.

The participant will be told if information becomes available that may be relevant to his/her willingness to continue participation in the study.

Each participant will be informed that a monitor or a health authority inspector, in accordance with applicable regulatory requirements, may review the portions of their source records and source data related to the study. Data protection and confidentiality will be handled in compliance with federal, state, local and university guidelines.

2. EXECUTIVE SUMMARY

Title of Trial

A multicenter, randomized, double blinded, placebo-controlled clinical trial of Anakinra (plus zinc) or prednisone in participants with severe alcoholic hepatitis by the AlcHepNet Consortium.

Name of Active Ingredient(s)

- a. Anakinra
- b. Prednisone
- c. Zinc-Sulfate

Pharmacological Class of the Drugs

- a. Anakinra is immunological agent, an inhibitor of the Interleukin-1 receptor (IL-1).
- b. Prednisone is an adrenal glucocorticoid.
- c. Zinc-sulfate is a nutritional supplement.

Indication

Severe alcoholic hepatitis.

Study Type

Phase 2B multicenter randomized, 2-arm, double blinded, placebo controlled clinical trial.

Investigational Sites

Indiana University, Mayo Clinic, Virginia Commonwealth University, Cleveland Clinic Foundation, University of Louisville, Beth Israel Deaconess Medical Center, University of Pittsburgh Medical Center, and University of Texas Southwestern Medical Center

Planned Number of Participants

Approximately 258 participants will be randomized in a 1:1 ratio into 1 of 2 treatment arms (129 participants per arm): (1) Prednisone + Placebo for Anakinra/Zinc (2) Anakinra + Zinc + Placebo for Prednisone.

Objectives

This multicenter, randomized, double blinded, placebo-controlled clinical trial is focused on novel treatments for severe alcoholic hepatitis (AH), a life-threatening stage of alcoholic liver injury that has a short-term mortality rate much higher than that of other liver diseases.

The primary objective of the study is to determine the clinical efficacy and safety of Anakinra (plus zinc) compared to the current standard medical treatment consisting of prednisone in participants with clinically severe AH. Key secondary objectives broadly are as follows: (a) to evaluate the use of biomarkers to assess disease severity and treatment response; and (b) to develop novel endpoints to overcome the limitations of current assessment strategies for severe AH.

Overview of Study Design and Conduct

The proposed study is a Phase 2b, multicenter, prospective, randomized, 2-arm, double blinded, placebo-controlled clinical trial to assess the efficacy of Anakinra, an interleukin (IL)-1 receptor antagonist plus zinc compared to prednisone for the treatment of severe AH (Model for End Stage Liver Disease (MELD) score ≥ 20). All participants will receive standard care for treatment of severe AH as described in recent guidelines endorsed by American Association for the Study of Liver Diseases (AASLD) and American Gastroenterological Association (AGA). The study will be conducted at 8 clinical sites across the United States selected by the National Institute of Alcoholic Abuse and Alcoholism (NIAAA) and will be supported by a Data Coordinating Center at Indiana University (DCC-IU). The biorepository will be managed by University of Massachusetts.

The study will be conducted according to Good Clinical Practice (GCP) and in compliance with local, state, and federal regulatory requirements. Adverse events during the course of the trial will be identified, recorded, assessed for causality, and reported in accordance with FDA guidance. In addition to general assessment, we will specifically focus on (1) rates and types of infection as well as their severity, (2) potential development of drug-induced liver injury, (3) injection site reactions, and (4) hematological adverse events.

This study will be approved by an appropriately convened single IRB, Western Institutional Review Board (WIRB), and will be monitored by an NIAAA appointed Data and Safety Monitoring Board (DSMB). We will conduct this study under an Investigational New Drug (IND) application from the United States Food and Drug Administration (FDA).

It is anticipated that a centrally located investigational pharmacy located at Indiana University will dispense the study medications to all participating sites under close coordination from the DCC-IU. Anakinra plus zinc, prednisone and matching placebos will be provided by the study to the participants.

Interventions to be tested

[figure not shown]
Concomitant treatments in this trial include standard care for severe AH for all participants as recommended in recent guidelines¹. The standard of care for severe AH includes attention to early diagnosis and treatment of bacterial and fungal infections, portal hypertension and its complications including acute kidney injury, gastrointestinal bleeding, fluid overload (ascites and edema) and hepatic encephalopathy.

In addition, all participants will be offered as part of the standard of care, non- pharmacologic intervention for treatment of alcohol use disorders, such as cognitive behavioral therapy and 12-step programs intervention as aligned with the best practices at the participating study site.

Participants with severe AH are very sick and often have multiple active medical problems requiring intervention. The use of specific interventions during this time has the potential to modify treatment response. Ideally, these interventions would be completely standardized. However, the standard of care varies by region, institution and the specialties involved in the care of the participant. The decision regarding treatments for these complications will be delegated to the primary physicians caring for the participants during hospitalizations and to the investigators during the ambulatory follow-up of the participants. Other than the general guidelines noted, no specific treatments for specific complications such as those noted are required. However, such treatments might include, but are not limited to, the administration of IV fluids, intravenous human serum albumin, antibiotics including antifungal medications, renal replacement therapy, supplemental oxygen, assisted ventilation and intravenous pressors. Diagnostic procedures such as paracentesis, upper endoscopy, colonoscopy, endoscopic ultrasound, and liver biopsy will be permitted as required to provide standard care.

During the initial six months of trial, the investigators will develop a “manual of clinical operations” that will include best practices on the use of vasopressors, albumin, ICU care, mechanical ventilation and renal replacement therapy using Surviving Sepsis Campaign, International Guidelines for Management of Severe Sepsis and Septic Shock. The investigators will also provide best practices for management of nutrition and alcohol counseling and minimization of recidivism. Although the management of these complications will not be mandated by protocol, the care provided will be recorded to develop novel designs for future trials and for practice guidance and quality improvement programs.

After informed consent has been obtained and all of the inclusion are met and none of the exclusion, participants will be randomized to receive one of the following interventions in addition to standard care.

[figure not shown]
Group 1: Standard of care **plus** prednisone 40 mg orally once daily on Days 1-30 and matching placebos for Anakinra (1 syringe s.c. once daily on Days 1-14), and zinc (matched pill once daily on Days 1-90).

Group 2: Standard of care **plus** Anakinra (100 mg s.c.) once daily on Days 1-14 zinc sulfate 220 mg once daily on Days 1-90, and placebo for prednisone (matched pill once daily on Days 1-30).

Lille score will be calculated from day 7 labs, participants will stop prednisone or prednisone placebo if Lille score >0.45.

Figure 1. Distribution of study drug and placebo

PHASE 2B, RANDOMIZED, CONTROLLED, DOUBLE-BLINDED TRIAL

* Stop prednisone/prednisone placebo if Lille score >0.45 at day 7

Participants or guardian will be instructed in subcutaneous injection technique to continue self-administration of these experimental treatments after discharge from the hospital. Study personnel will ensure participants and guardian are proficient in the technique before the end of study visit and an instructional document will be provided.

Primary and Important Secondary Endpoints

Primary Endpoints Survival at 90 days

Secondary Endpoints

- **Changes in score(s):** Changes in Lille score, change in MELD score, development of AKI, multi-organ failure, SIRS, transfer to ICU, changes in liver function will all be evaluated at 7, 30 and 90 days.
- **Organ dysfunction:** Measure of changes in Sequential Organ Failure Assessment (SOFA) scores and proportions requiring hemodynamic support for MAP < 65 mm Hg and lactate > 2 mmol/l, renal replacement therapy or mechanical ventilation. The SOFA score will be modified and re-evaluated without platelet counts given that these are usually low in AH.
- **Infections and Sepsis:** The endpoints and case definitions related to sepsis may vary depending on what will be used (clinical care, research, surveillance or quality improvement). Given the central role of sepsis as a driver of outcomes, measuring the types of infection will occur but also identify the proportions of those with sepsis, septic shock or quick-SOFA (qSOFA) criteria based on SEPSIS-3 guidance^{2,3}. Key parameters will be captured and needed for various sepsis related endpoint construction aligned by the recent guidance from the European Drug Development Hub (<http://eddh-cro.wixsite.com/fdtfsv>).
- **Renal dysfunction:** In alignment with guidance from the acute disease quality initiative, the AKI development will be quantified and its progression through persistent AKI, acute kidney disease to chronic kidney disease.
- **Need for care escalation:** Proportion of participants requiring transfer to ICU for care, intubation for airway control, need for ventilator support or RRT.
- **Indicators of gut permeability:** (endotoxin and bacterial 16S DNA) and pro-inflammatory cytokine/chemokines (TNF α , MCP1, IL-6, IL-1 β) will be assessed in serum/plasma samples.
- **Survival at 30 days and 180 days**

Limitations of mortality as an endpoint in AH and plans to overcome these

All-cause mortality is most relevant when mortality is substantial and attributable to a single mechanism in a homogeneous population. Participants with severe AH are highly heterogeneous with respect to disease severity, end organ involvement and the care they receive. Moreover, as in sepsis and heart failure, death involves failure of multiple organs (liver, heart, kidney, lungs) making it difficult to ascertain which one is the primary cause of death. This has led to development and regulatory acceptance of composite endpoints including mortality and key parameters driving mortality for acute heart failure trials. These guiding principles to construct a novel and innovative key secondary composite endpoint which will include death or worsening of the modified SOFA score^{4,5} by ≥ 2 points and worsening of MELD score by ≥ 2 points. These are associated with mortality and capture the organ recruitment that marks progression of AH towards death. This endpoint will also be validated with respect to reliability, construct-, criterion- and content validity to establish this as a primary endpoint in future trials. Model changes in SOFA scores and MELD scores against mortality to further optimize this endpoint and cross-validate it in the observation cohort will occur.

Novel (experimental) endpoints to overcome limitations of conventional endpoints Efficacy endpoints must capture “clinically meaningful benefit”. While traditional endpoints such as mortality are meaningful, they also have multiple shortcomings in the context of AH as noted below. Innovation will be used to construct, measure, and validate novel additional endpoints to overcome the limitations of currently used endpoints and cross-validate them in the observational cohort. The combined expertise in endpoint development and the use of harmonized measurements will make this feasible. These will provide novel assessments in AH and provide the scientific evidence-base to use these as primary endpoints in future trials.

Inclusion Criteria

1. AH, as defined by the NIAAA pan-consortia for AH⁶:
 - a) Onset of jaundice (**defined as serum total bilirubin >3mg/dL**) within the prior 8 weeks to screening visit
 - b) Regular consumption of alcohol with an intake of > 40 gm daily or >280gm weekly on average for women and > 60 gm daily or >420gm weekly on average for men for 6 months or more, with less than 8 weeks of abstinence before onset of jaundice
 - c) AST > 50 IU/l
 - d) AST: ALT > 1.5 and both values < 400 IU/l
 - e) and/or histological evidence of AH*
2. MELD 20-35 on day of randomization.
3. Ages ≥ 21

**In patients with possible AH or AH with confounding factors such as possible ischemic hepatitis, possible DILI, uncertain history of alcohol use (e.g., patient denies excessive alcohol use), and atypical/abnormal laboratory tests (e.g., AST < 50 IU/L or > 400 IU/L, AST/ALT ratio < 1.5), antinuclear antibody > 1:160 or SMA > 1:80, a standard of care liver biopsy may be performed during current hospital admission to confirm AH and exclude competing etiologies¹⁷*

Exclusion Criteria

1. MELD SCORE <20 or > 35
2. Active sepsis (positive blood or ascitic cultures) with Systemic Inflammatory Response Syndrome (SIRS) or hemodynamic compromise requiring intravenous pressors to maintain tissue perfusion
3. Pneumonia as evidenced by radiological exam
4. Multi-organ failure
5. Renal failure defined by GFR <35 mL/min by CKD- EPI.
6. Clinically active C. diff infection
7. History of imaging of the liver (ultrasound, computerized tomography, or magnetic resonance) showing other causes of jaundice
8. History of other liver diseases including hepatitis B (positive HBsAg or HBV DNA), hepatitis C (positive HCV RNA), autoimmune hepatitis, Wilson disease, genetic hemochromatosis, alpha1-antitrypsin deficiency, or strong suspicion of Drug Induced Liver Injury (DILI). Previously treated hepatitis C that was cured (sustained virological response with negative RNA \geq 24 weeks following treatment) is not an exclusion.
9. History of HIV infection (positive HIV RNA or on treatment for HIV infection)
10. History or presence of cancer (including hepatocellular carcinoma) other than non-melanoma skin cancer
11. History of other significant medical problems such as autoimmune diseases, severe asthma, psoriasis, Inflammatory Bowel Disease (IBD), etc. that might require immunosuppressive treatments
12. Pregnancy or breastfeeding
13. Prior exposure to experimental therapies in last 3 months
14. Prior exposure to systemic corticosteroid (glucocorticoid) or immunosuppressive therapy for more than 4 days within previous 30 days
15. Need for inotropic pressor support to maintain perfusion to critical organs within prior 48 hours before randomization and initiation of experimental treatment
16. Clinically significant pancreatitis- abdominal pain, elevated lipase ($> 3 \times$ ULN) and at least edema of pancreas with fat-stranding on CT scan
17. Total WBC count $> 30,000/\text{mm}^3$
18. Known allergy or intolerance to therapeutic agents to be tested
19. Inability to voluntarily obtain informed consent from participant or guardian
20. Perceived inability to follow study procedures and comply with protocol
21. Platelet count $< 40,000 \text{ k/cumm.}$
22. Positive PCR test for COVID -19 within 7 days prior to the baseline day 0 visit*
23. Active gastrointestinal bleeding defined as hematemesis or melena with a decrease in hemoglobin more than 2 g/dl in 24 hrs. Due to gastrointestinal bleeding, or with a decrease in mean arterial BP to $< 65 \text{ mmHg}$

**Positive PCR test for COVID-19 is exclusionary only during screening period. If a patient tests positive any time after baseline randomization, a positive PCR test for COVID-19 will be considered as a SAE.*

The participants for this study will be recruited from a hospitalized population of participants meeting the eligibility criteria outlined above who live within one day travel from one of the

participating clinical centers and who have provided informed consent to participate in this clinical trial and who are willing to continue their participation for the anticipated follow-up period of the trial. Although the primary endpoint is survival at 90 days, follow-up visits will be continued up to 6 months.

Study Visits and Data Collection Schedule*****

	Screening	Treatment Phase							Follow-up phase
		D0	D3	D7	D14	D28	D60	D90	
Window (days)		±2	±2	±2	±2	±7	±7	±7	±7
Informed consent	x								
History and physical	x	x	x	x	x	x	x	x	x
Vital signs, weight ***	x	x	x	x	x	x	x	x	x
Alcohol consumption history	x	x			x	x	x	x	x
Randomization		x							
Concomitant medicines	x	x	x	x	x	x	x	x	x
Dispense Study Drug		x		*					
Adverse events			x	x	x	x	x	x	x
Electrocardiogram** ****	x								
Evaluation of compliance			x	x	x	x	x	x	
CBC, PT/INR, Hepatic Function Panel, BMP	x	x	x	x	x	x	x	x	x
Test for COVID-19****	x								
Sepsis studies, as indicated	x	x	x	x	x	x	x	x	x
Pregnancy test, serum**	x								
Pregnancy test, urine**		x			x	x	x	x	x
Blood collection for trough Anakinra levels		x	x	x	x				
Specimen Banking¶		x		x	x	x	x	x	x
Saliva Banking+		x						x	
Questionnaires δ	x					x	x	x	x

¶ Specimen banking includes blood and stool (when possible) D0, D7, D14, D28, D60, D90, D180, and, when available, urine and liver biopsy/tissue. Blood will be used to extract germline DNA at baseline and at Day 180 as well as to extract serum/plasma/PBMC at all visits. *Type of specimen collection is site specific.*

+ Saliva collection at D0 and D90. Collected until an adequate number of samples are collected.

δ Questionnaires include Alcohol Use Disorders Identification Test (AUDIT), Alcohol Timeline Follow Back (TLFB), and Chronic Liver Disease Questionnaire (CLDQ). The timeline follow back questionnaire will be the only questionnaire administered at days 28, 60, 90, and 180. All are given at screening.

*Day 7 study drug dispensation will be unscheduled and only on an as-needed basis, based on safety lab evaluations (**outpatient only.**)

** if applicable

*** height at screening only.

**** Test for COVID-19 PCR only if not done as SOC with 7 days prior to the baseline Day 0 visit.

***** In response to COVID-19, we are lessening restrictions if applicable or necessary such as: allowing wider windows D14, D28, D60 to +/- 10 days. Allowing replacement of protocol mandated in-person study visits with one or more of the following, phone calls, telemedicine virtual visits, implement digital technology to record responses to questionnaires. Lastly, allowing blood draws at remote or commercial laboratories

*****ECG can be done as standard of care within 7 days of screening

Abbreviations: CBC: Complete blood count, BMP: Basic metabolic, INR: International normalized ratio and PT: Prothrombin Time.

Data Collection

Clin= clinical (relevant elements of history, physical exam), Biosamples: whole blood, plasma, serum, PBMC, DNA, and stool (when possible) at all time-points, liver biopsy/tissue and urine (20ml) if available, Questionnaires= AUDIT, alcohol timeline follow back, CLDQ, SOC (standard of care) labs= CBC, Hepatic Function Panel, BMP: Basic Metabolic Panel, PT/INR, Sepsis studies at baseline and during trial duration, as indicated (blood cultures, chest X ray, stool for WBC and C. Diff as indicated, ascites tap, UA with culture, liver ultrasound or other imaging, endoscopy if available within 6 months).

Relevant clinical care parameters will be recorded on days specified. As noted above, attention will be paid to recording concomitant care provided to treat complications related to AH and/or portal hypertension including those treatments not specified by protocol, including but not limited to antibiotics, IV fluids, albumin, pressors, renal replacement, etc.

Standardizing study conduct and good clinical practice (GCP)

Variations in protocol implementation and clinical care can have a major impact on trial outcomes. This will be optimized by: (1) GCP training and certification of all study personnel, (2) investigator/coordinator training and certification prior to site activation, (3) monthly performance reports, (4) development of manual of operations that provide best practices, and (5) annual investigator meeting to review developments and clinical and trial practice patterns. (6) DSMB will convene every 6 months to ensure relevant study procedures are followed.

Study Population

The study population will be comprised of men and women of all races, ethnic groups and socioeconomic status of the ages of 21 and greater admitted to the hospital with a clinical diagnosis of AH. A full description of the statistical analysis and calculation of sample size is recorded below. The definition of AH is established by the NIAAA pan-consortia for AH. A conscious decision not to require a liver biopsy for inclusion was made based on the current low rate of liver biopsy used to establish this diagnosis in the US and the ability to diagnose the condition with relative accuracy based on the experience in the first cycle of funding. Eligible participants will be identified based on inclusion/exclusion criteria as defined above.

Enrollment sites

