2.3 Summary of Known Potential Risks with Study Medication

Corticosteroids (including prednisone) are the standard medical care for severe acute AH and have anti-inflammatory effects that can alter the body's reaction to other injuries. Prednisone may cause some, all or none of the side-effects listed below at the dose and duration used in the study.

Side effects	Frequent >20% of participants	Occasional 2 - 20% of participants	Rare Less than 2% of participants
Serious	Infection	Psychosis, Pancreatitis, Ulcerative esophagitis, Cushing's syndrome	Anaphylaxis, Hypersensitivity reaction, Peptic ulcer, Bone necrosis, Blood clot in a deep vein
Less Serious	Weight gain	High blood sugar, High blood pressure, Wound healing impairment, Increased intraocular pressure, Increased liver enzymes	Muscle weakness
Minor	Facial swelling Fluid retention Indigestion Increased appetite	Difficulty sleeping, Mood changes, Euphoria, Headache, Bruising	

Anakinra (study drug) is another anti-inflammatory treatment. It can alter the body's reaction to other injuries. Anakinra may cause some, all or none of the side-effects listed below at the dose and duration used in the study.

Side Effects	Frequent >20% of participants	Occasional 2 - 20% of participants	Rare Less than 2% of participants
Serious		Infection, including cellulitis, pneumonia and bone and joint infections)	Anaphylaxis, hypersensitivity reactions, Angioedema, Malignancy
Less Serious		Low blood count, (Neutropenia), Joint pain	Low blood count (Eosinophilia, Platelets), Nausea, Diarrhea
Minor	Injection site redness	Fever, Nasopharyngitis, Skin rash	

Zinc is an essential nutrient found in highest quantities in oysters, shellfish, meat, chicken, and fish. It is essential for the body's cells to function. When given in tablets, zinc may cause some, all or none of the side-effects listed below at the dose and duration used in the study.

Side effects	Frequent >20% of participants	Occasional 2 - 20% of participants	Rare Less than 2% of participants
Serious			
Less Serious	Nausea, Vomiting, Dizziness, Headache, Abdominal cramps, Diarrhea		
Minor	Indigestion		

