4. INVESTIGATIONAL PLAN

4.1 Overall Trial Design and Plan

Overview of Study Design and Conduct

The proposed study is a Phase 2b, multicenter, prospective, randomized, 2-arm, double blinded, placebo-controlled clinical trial to assess the efficacy of Anakinra, an IL-1 receptor antagonist plus zinc compared to prednisone for the treatment of severe AH (Model for End Stage Liver Disease (MELD) score ≥ 20). All participants will receive standard care for treatment of severe AH as described in recent guidelines endorsed by AASLD and AGA¹. The study will be conducted at **8 clinical sites** across the United States selected by the NIAAA and will be spearheaded by a **Data Coordinating Center (DCC-IU) at Indiana University**.

The study will be conducted according to good clinical practice (GCP) and in compliance with local, state, and federal regulatory requirements. Adverse events during the course of the trial will be identified, recorded, assessed for causality, and reported in accordance with FDA guidance. In addition to general assessment, we will specifically focus on (1) rates and types of infection as well as their severity, (2) potential development of drug-induced liver injury, (3) injection site reactions, and (4) hematological adverse events. These are related to the mechanisms of action of the drugs to be tested.

It is anticipated that this study will be approved by an appropriately convened single IRB and will be monitored by an NIAAA appointed data and safety monitoring board. We will conduct this study under an Investigational New Drug (IND) application from the United States Food and Drug Administration (FDA).

It is anticipated that a centrally located investigational pharmacy located at Indiana University will dispense the study medications to all participating sites under close coordination from the DCC- IU. Anakinra plus zinc and prednisone and matching placebos will be provided by the study to the participants.

Interventions to be tested

Concomitant treatments in this trial include standard care for severe AH for all participants as recommended in recent guidelines. The standard of care for severe AH includes attention to early diagnosis and treatment of bacterial and fungal infections, portal hypertension and its complications including acute kidney injury, gastrointestinal bleeding, fluid overload (ascites and edema) and hepatic encephalopathy. As part of the standard of care, all participants will be offered non-

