9.2 Physical Examination and Vital Signs

To assess for clinical findings, the investigator or designee will perform a physical examination at the time points specified in the Schedule of Trial Procedures (Table 1). All above physical exams may be extracted from medical records if patient is inpatient. This includes height only at Screening. The physical examination must include the following:

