9.2.1 Physical Examination

- General appearance
- Weight
- Eyes
- Ears, nose, and throat
- Neck
- Respiratory system
- Cardiovascular system
- Abdominal region
- Mental status
- Neurological system

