10. ADVERSE EVENTS

10.1 Definition of Adverse Events & Reporting Period for Adverse Events

Safety will be assessed in terms of AEs. All AEs, whether observed by the investigator, reported by the participant, noted from laboratory findings, or identified by other means, will be recorded from Day 0 until the participant completes trial participation (D-180).

AEs are defined as any untoward medical occurrence associated with the use of the study medication in humans, whether or not considered related to study medication. An AE (also referred to as an adverse experience) can be any unfavorable and unintended sign (e.g., an abnormal laboratory finding), symptom, or disease temporally associated with any use of the study medication, without any judgment about causality and irrespective of route of administration, formulation, or dose, including an overdose. For this trial, study medication refers to Anakinra, zinc, Prednisone, or placebo in the double-blind phase.

AEs include but are not limited to: (1) a worsening or change in nature, severity, or frequency of condition(s) present at the start of the trial; (2) participant deterioration due to primary illness; (3) intercurrent illness; and (4) drug interaction.

Participants should be questioned in a general way, without leading the participant or asking about the occurrence of any specific symptom. The investigator should attempt to establish a diagnosis of the event based on signs, symptoms, and/or other clinical information. The diagnosis and not the individual signs/symptoms should be documented as the AE. For example, if the underlying disease process is a stroke, it would not be appropriate to record the AE by describing the symptoms “sudden numbness, dizziness, and difficulty speaking.” The AE medical term of “stroke or cerebrovascular accident” should be recorded as it more accurately describes the AE. Following questioning and evaluation, all AEs, whether believed by the investigator to be related or unrelated to the study medication, must be documented in the participant’s medical records, in accordance with the investigator’s normal clinical practice and on the AE source Document. Each AE is to be evaluated for duration, intensity, frequency, seriousness, outcome, other actions taken, and relationship to the study medication.

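### Injection site reactions are a declared safety focus, but the plan gives no systematic way of finding them, so the recorded rate may be too low and uneven between sites

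*Combined protocol and SAP*

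**What the plan says.** **The promise.** The Executive Summary and section 4.1 name four events for special attention in addition to general safety assessment: infection, then "potential development of drug-induced liver injury, (3) injection site reactions, and (4) hematological adverse events". Section 4.1 gives the reason: "These are related to the mechanisms of action of the drugs to be tested". Section 2.3 puts "Injection site redness" in the anakinra table under more than 20% of participants, in the row for minor effects. No other anakinra effect is in that frequency column.

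**The collection rules.** Section 10.1 states: "Participants should be questioned in a general way, without leading the participant or asking about the occurrence of any specific symptom". It makes no exception for the four focus events. The same section also states: "All AEs, whether observed by the investigator, reported by the participant, noted from laboratory findings, or identified by other means, will be recorded".

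**The examination.** Section 9.2 introduces the list in 9.2.1 with "The physical examination must include the following". The list has ten items. One is "Abdominal region"; none is skin or injection site. Section 9.2 adds: "All above physical exams may be extracted from medical records if patient is inpatient".

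**The setting.** Section 6.4 has daily injections on Days 1 to 14, active or placebo according to arm. Section 4.1 has participants or guardians take over the injections after discharge. Table 1 and sections 7.2.3 to 7.2.5 place an examination and an AE assessment at D3, D7 and D14, with no injection-site row or procedure.

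**The concern.** A focus that goes beyond general assessment needs a collection method that goes beyond general assessment. For injection site reactions the protocol text supplies only the general one: an open question, an examination with no relevant item, and whatever else is noticed.

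The consequence is a recorded rate that depends on how attentive each site is and on whether participants mention a mild local reaction while seriously ill. Safety is part of the stated primary objective, and this is a comparison of active with placebo injections. If the same fraction of reactions is captured in both arms, the absolute difference between arms shrinks by that fraction. If the fraction differs by site, the pooled rate becomes hard to interpret.

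**Working it through.** The plan states no sample size, power or precision for injection site reactions, so there is no figure to reproduce. The check is a comparison of sections, followed by an illustration.

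**Step 1. How each focus event is ascertained.**

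| Focus event | Provision in the protocol |
|---|---|
| Infection | Case definitions in 5.4.1, 6.6.1 and 10.2.2; sepsis studies in Table 1 |
| Drug-induced liver injury | MELD, Child's score, ALT and alkaline phosphatase thresholds in 5.4.2 and 6.6.1; scheduled labs |
| Hematological events | CBC at every visit in Table 1; platelet and leukocyte rules in 6.6.1 |
| Injection site reactions | No definition, examination item, schedule row, diary or separate analysis |

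The gap is specific to the fourth event.

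**Step 2. How far the general routes reach.** D3, D7 and D14 nominally fall within the 14-day injection period, so an investigator has three chances to see a reaction. Four provisions weaken this:

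- Inpatient examinations may come from the chart, which holds only what ward staff wrote down.
- After discharge, staff do not see each injection.
- The COVID-19 footnote to Table 1 allows phone or telemedicine visits and widens the D14 window to ±10 days. The latest D14 visit is then Day 14 + 10 = Day 24, ten days after the last injection.
- Under 7.2.8, a missed visit becomes a phone call or a record review.

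At a remote visit, the open question is the main route left.

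**Step 3. Illustration of size.** Inputs: 129 participants per arm (Executive Summary) and a true rate of 20%, the lower edge of the frequent class in 2.3. The capture fraction c is an assumption; the documents give none.

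Expected recorded count = 129 × 0.20 × c; recorded rate = 0.20 × c; Wilson 95% intervals.

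| c (assumed) | Recorded count | Recorded rate (95% interval) |
|---|---|---|
| 1.00 | 25.8 | 20% (14–28%) |
| 0.90 | 23.2 | 18% (12–26%) |
| 0.75 | 19.4 | 15% (10–22%) |
| 0.50 | 12.9 | 10% (6–16%) |

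With equal capture in both arms, recorded difference = c × true difference. If the true rates were 25% and 5% (both assumed), the 20-point difference would be recorded as 18, 15 or 10 points at c = 0.90, 0.75 or 0.50. The 5:1 ratio would not change.

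**Step 4. Would uneven capture show in the data?** With 8 sites and equal enrolment (assumed), a site has 129 / 8 ≈ 16 anakinra participants. At 20% that is 16.1 × 0.20 ≈ 3 with a reaction. Counts this small could not separate poor capture at one site from chance.

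**The case against.** **The rule does not forbid capture.** Section 10.1 is worded as a recommendation and concerns verbal questions about symptoms. Redness is a visible sign. The same section requires AEs seen by the investigator or found by any other route to be recorded, and the 9.2.1 list is a minimum. Participants start in hospital, so home injection covers only the days left after discharge. This stands. A reader might infer that only volunteered or charted reactions will be recorded, and that under-recording is certain. The documents do not support either inference.

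**Part of the machinery exists.** Every AE is graded by Table 2, and 11.3.1 tabulates treatment-emergent AEs by preferred term, arm and severity. This stands too. Only the prompt to look, and a separate display of what it finds, would be new.

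**A prompt may sit elsewhere.** The CRF, the AE source document, the manual of operations and the phone script are not among the documents reviewed. Any of them might contain one. In that case 10.1 would conflict with it and would still need an exception.

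**The event is of low consequence.** It is classed as minor, and no endpoint, interim rule or sample size depends on it. This limits the weight of the point. Section 2.3 is also a risk list, not a forecast for this trial.

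**Open questioning is deliberate, and a check has a cost.** Non-leading questions guard against suggestion. A mandated look at the injection site may give the assessor a clue to treatment arm. That matters little for all-cause death itself. It could affect causality ratings and outcomes that investigators influence, such as ICU transfer, and possibly the transplant decisions that censor the primary analysis. This stands as a reason to design the check carefully, but not as a reason to leave a named focus without one.

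**Conclusion.** The point holds as a minor one. The protocol names injection site reactions as one of four safety foci, lists redness as the only frequent anakinra effect, and provides no systematic ascertainment of it. The recorded rate may be too low and may vary between sites, most of all for mild reactions after discharge.

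How much too low cannot be derived from the documents. The recorded rates of 18%, 15% and 10% in the illustration rest entirely on assumed capture fractions. Nor does the recorded rate have to fall below the protocol's own 20% class: at a true 25%, it does so only if c is below 0.20 / 0.25 = 0.80. With equal capture, the ratio between arms is preserved and only the absolute difference shrinks. The conclusion also assumes that the unseen CRF and manuals contain no injection-site prompt.

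**What to change.** 1. Add one standard injection-site item, present or absent, at the existing D3, D7 and D14 visits in both arms. Use direct inspection, not chart extraction, when the visit is in person, and one neutral, fixed question when it is remote. The Table 2 grade already applies to any reaction found.
2. In 10.1, add a sentence exempting this item from the general-questioning rule.
3. In 11.3.1, report the item by arm, separately from spontaneously reported AEs, so that the two methods of ascertainment are not mixed.
4. Where feasible, have the item recorded by staff who do not rate causality.

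The cost is one CRF line, one sentence in 10.1, one table and a short addition to three existing visits. No visit is added. The main downside is the possible clue to treatment arm; item 4 reduces it but does not remove it, and smaller sites may not have a separate assessor. A remote question will be less reliable than inspection, so the mode of assessment should be recorded with the result.
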